5.3. Clinical Experience

Daré's drug product DARE-VVA1 has not been tested before in humans. Previously, an exploratory study of vaginal tamoxifen has been conducted in 4 healthy postmenopausal women, in which a vaginal suppository containing 13 mg tamoxifen was formulated by a compounding pharmacist.¹⁷ Participants self-administered the suppository once a day for 1 week, before moving to a twice-per-week schedule. Blood concentrations of tamoxifen were measured at 8 weeks, with samples collected 5 hours after insertion. Additional assessments included measurements of vaginal pH and improvement of vaginal dryness, and monitoring of adverse events (AEs).

After 3 months of treatment, the median vaginal pH was 5.0 (range: 5.0 to 5.2), compared to 7.1 (range: 6.5 to 7.5) at baseline, with a median paired difference of 2.0 (range: 2.5 to 1.5). Self-assessments of dryness using a visual analog scale from 0 (participant not bothered by dryness) to 10 (participant extremely bothered by dryness) showed an improvement, from a median score of 8 (range: 7.5 to 9.0) at baseline to 3.0 (range: 2.0 to 3.0) after 3 months, with a median paired difference of 5.5 (range: 6.0 to 4.5).

All 4 participants completed the 3-month treatment period. No AEs were reported, and there were no changes to vital signs. Measurements of blood concentrations of tamoxifen at 8 weeks were conducted for all 4 participants; the median plasma concentration of tamoxifen was 5.8 ng/mL (range: 1.0 to 10.0 ng/L). In comparison, after once daily oral treatment with 20 mg tamoxifen for 3 months, the average steady state plasma concentration of tamoxifen is 122 ng/mL (range 71.0 to 183.0 ng/mL).¹⁶

This exploratory study demonstrated that vaginal administration of tamoxifen represents a possible new treatment approach for postmenopausal women with VVA. With this route of administration, tamoxifen demonstrated clinically relevant physiological changes, while systemic absorption of the study drug was not clinically relevant, with systemic exposure less than 10% of that seen when the same dose is administered orally.¹⁶ The local action of tamoxifen on the vaginal epithelium suggests that the parent compound itself is estrogenic and not metabolized locally in the vaginal epithelium, but predominantly systemically into anti-estrogens. Together, these results suggest that tamoxifen could be beneficial for the treatment of VVA in patients who are at risk of breast cancer, due to its local activity as an estrogen, and systemic activity as an estrogen antagonist.

5.4. Summary of Potential Risks and Benefits

The potential benefits of study participation are that participants with VVA may experience a reduction in the symptoms associated with VVA as a result of treatment with DARE-VVA1. No other benefits of participation are anticipated.

The potential risks of study participation include those associated with exposure to tamoxifen and the excipients found in DARE-VVA1 and the risks of medical evaluation, including venipuncture.

Oral tamoxifen (tablets or solution) is approved for the treatment of estrogen receptor-positive metastatic breast cancer and to reduce the risk of breast cancer in women at high risk.¹⁸ The label includes a boxed warning concerning the risk of uterine malignancies, stroke, and pulmonary embolism. General warnings include risks of thromboembolic events (although this risk is greater when co-administered with chemotherapy), embryo-fetal toxicity (which is not a risk in the present study population), and liver cancer and liver abnormalities.

The National Surgical Adjuvant Breast and Bowel Project reported relative risks of serious events in a double-blind, placebo-controlled study of 5 years' treatment with tamoxifen (20 mg per day) designed to evaluate whether treatment would reduce the incidence of invasive breast cancer in high-risk women. After a median treatment duration of 3.5 years in 13,388 women, the rates (per 1,000 women per year) for major outcomes were as follows:

Major Outcomes	Rates for tamoxifen (per 1,000 women per year)	Rates for placebo (per 1,000 women per year)
Endometrial adenocarcinoma	2.20	0.71
Uterine sarcoma	0.17	0.0
Stroke	1.43	1.00
Pulmonary emboli	0.75	0.25
Deep vein thrombosis	1.26	0.79
Cataracts	25.41	22.51

Source: Soltamox label¹⁸

In addition to these serious risks, the most common adverse reactions with oral tamoxifen include hot flashes, mood disturbances, vaginal discharge, vaginal bleeding, nausea, and fluid retention.¹⁸

In the present study, steps will be taken to reduce the risks associated with the use of tamoxifen. In addition to limiting the treatment duration to 56 days, and to the reduction of systemic exposure afforded by the use of intravaginal administration, the present study has been designed with eligibility criteria that will exclude participants who might be at particular risk of experiencing the more serious side effects of tamoxifen, while regular safety monitoring will be performed. Eligible participants who have not undergone hysterectomy will have no history of endometrial ablation or endometrial hyperplasia, with ultrasound at screening showing endometrial thickness ≤ 4 mm. Participants with a cervix will also have an up-to-date cervical cancer screening record. All participants must have a normal mammogram within 2 years of screening; participants who have not had a mammogram in the last 2 years, or have a cervix but have not had a cervical screening test (CST) in the last 5 years, will be required to undergo these assessments during screening.

Participants will be excluded if they have any of the following: a history of coagulopathies, thrombophilia, thromboembolic disease, or significant transient ischemic attack; significant cardiac history; recent history of breast cancer (or suspicion of breast cancer), abnormal cervical screening result within 2 years; endometrial pathology; known or suspected estrogen-dependent neoplasia. Safety monitoring will include 12-lead electrocardiograms (ECGs) to evaluate possible cardiac problems; laboratory assessments will include measurement of liver functions tests and clotting parameters, to monitor hepatic safety and potential embolism/thrombotic events, respectively; and regular vaginal inspection. Due to the reported risks of endometrial adenocarcinoma and uterine sarcoma, transvaginal ultrasounds will be performed at screening on women who have not undergone hysterectomy in order to measure endometrial thickness.

In the present study, participants allocated to active treatment will receive tamoxifen intravaginally for 56 days, at doses ranging from 1 mg per day to 20 mg per day for 2 weeks, before moving to a twice-weekly regimen. Administration of tamoxifen by intravaginal inserts is expected to yield significantly lower systemic concentrations of tamoxifen than oral administration. In an exploratory study, 4 women were treated with vaginal suppositories containing 13 mg tamoxifen once daily for 1 week then twice a week thereafter. Participants' systemic plasma concentrations (sample taken 5 hours post last dose following 8 weeks of treatment) ranged from 1.0 to 10.0 ng/mL¹⁷; in comparison, an average steady-state concentration of 122 ng/mL was observed with 20 mg oral tamoxifen once daily for 3 months.¹⁶

Although long-term treatment with tamoxifen is associated with risks of serious adverse effects, the risks associated with 56 days' treatment with tamoxifen are considered minimal. In comparison, the potential reduction of VVA symptoms could be beneficial to participants, with these symptoms affecting numerous aspects of women's lives, such as sex life, self-esteem, and relationships, in addition to the improvement in physical health.¹⁹

A summary of the pharmaceutical properties and known potential risks of DARE-VVA1 is provided in the current version of the Investigator's Brochure (IB). The investigator must become familiar with all sections of the DARE-VVA1 IB before the start of the study.

6. OBJECTIVES

6.1. Primary Objective

The primary objectives are:

- To evaluate the safety and tolerability of DARE-VVA1 by intravaginal administration
- To determine the plasma pharmacokinetics (PK) of DARE-VVA1 after intravaginal application

6.2. Secondary Objectives

The secondary objective is:

- To evaluate preliminary efficacy and pharmacodynamics (PD) in terms of most bothersome symptom, dyspareunia, and changes in vaginal cytology and pH

6.3. Exploratory Objectives

The exploratory objective is:

- To evaluate the impact of DARE-VVA1 on quality of life using a menopause-specific instrument
- To assess the usability and acceptability of DARE-VVA1

6.4. Objectives and Endpoints

Objectives	Endpoints
Primary	

 • To evaluate the safety and tolerability of DARE-VVA1 by intravaginal administration 	
 • Adverse events • Clinical laboratory findings • Vital signs results • 12-lead ECG results • Physical examination findings • Change in local site irritation scores from baseline to Day 57 • Endometrial thickness (measured by transvaginal ultrasound) in women who have not undergone hysterectomy prior to the study

 • To determine the plasma PK of DARE-VVA1 after intravaginal application 	
 • Standard PK parameters from noncompartmental analysis on Day 1, with steady-state parameters on Day 56 • Dose-proportionality of tamoxifen

Secondary	

 To evaluate preliminary efficacy and pharmacodynamics of DARE-VVA1 in terms of most bothersome symptom, dyspareunia, and changes in vaginal cytology and pH 	
 Change of vaginal pH from baseline to Day 57 Change in vaginal cytology (maturation index; percentage of basal and superficial cells) from baseline to Day 57 Change in most bothersome symptom from baseline to Day 56 Change in severity of dyspareunia from baseline to Day 56 Correlation between exposure and local changes
Exploratory	

 To evaluate the impact of DARE-VVA1 on quality of life using a menopause-specific instrument To assess the usability and acceptability of DARE-VVA1 	
 Change in the MENQOL questionnaire from baseline to Day 57 Responses to the Usability and Acceptability questionnaire over time

[figure not shown]

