CRITERIA FOR EVALUATION	
Pharmacokinetics:
 
After baseline evaluations including the time 0 venous plasma sample, the Day 1 DARE-VVA1 dose or matching placebo will be administered. Serial peripheral venous samples will be drawn from an indwelling line at 0.5, 1, 2, 4, 5, 8, 12, and 24 hours. The same sampling schedule will be used for PK analysis with administration of the Day 56 vaginal insert. Trough samples will be collected before administration of inserts on Days 4, 7, 10, 18, 28, and 42, and a final sample will be collected at follow-up on Day 63.
 
Samples will be analyzed using validated methods to determine plasma concentrations of tamoxifen and 3 metabolites: 4-hydroxytamoxifen, N-desmethyltamoxifen, and N-desmethyl-4-hydroxytamoxifen (endoxifen).
 
Safety:
 
Observations of safety (self-reported or by examination) will be recorded on an ongoing basis. Any irritation, discharge or pain will be reported as an adverse event (AE) using standardized Medical Dictionary for Regulatory Activities (MedDRA) codes and graded for severity.
 
Visual examination by vaginal speculum and full pelvic examination for any vaginal inflammation will be conducted at screening, pretreatment (Day 1), during treatment, and 1 week after treatment.
 
Clinical laboratory measurements including full hematology and biochemistry panels will be recorded at screening, at baseline, on Days 7, 18, 28, and 57, and 1 week after treatment.
 
Dipstick urinalysis of a void sample will be reported at screening, at baseline, on Days 7, 18, 28, and 57, and 1 week after treatment. If abnormal, the sample will be centrifuged for microscopic description of cellular elements.
 
Vital signs, including pulse rate, respiratory rate, and supine blood pressure, will be recorded in a supine position at screening, during the administration period, and 1 week after treatment.
 
Standard 12-lead ECGs will be recorded at screening, prior to dose on Days 1, 7, 18, 28, and 56, at 4 hours postdose on Days 1 and 56, on Day 57, and 1 week after treatment.

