- c. Participants will be discharged from the site after all 24-hour assessments have been completed. Day 1-2 only: Administration of DARE-VVA1 should be the final activity before discharge, following completion of all 24-hour assessments.
- d. A complete physical examination (excluding rectal examinations) will be performed at screening and will include a manual breast examination. Subsequent physical examinations will be abbreviated and will be directed based on signs and symptoms exhibited by the participant.
- e. Vaginal speculum examinations will include assessment of local irritation (scoring of erythema and edema), and a full pelvic examination.
- f. Mammograms should be conducted ONLY in those participants who have not had one within the last 2 years.
- g. Cervical screen testing should be conducted ONLY in those participants who have a cervix and have not had cervical screening within the last 5 years.
- h. Vital signs assessments will include pulse rate, respiratory rate, and supine blood pressure. Assessments will be performed after the participant has been in a supine position for at least 5 minutes. Temperature will also be measured.
- i. 12-lead ECGs will be performed after the participant has been supine for at least 5 minutes.
- j. FSH will be assessed in all hysterectomized women who have not undergone bilateral oophorectomy, and in non-hysterectomized women who have not undergone bilateral oophorectomy and have experienced spontaneous amenorrhea for ≥ 6 months but < 12 months, to confirm postmenopausal status.
- k. Drugs of abuse will be measured at screening by local laboratories via urinalysis and alcohol screens versus a commercially available urine dipstick.
- l. Viral serology: a blood sample will be collected for the determination of HIV, HCV, and HBsAg.
- m. Vaginal pH will be evaluated using commercially available pH strips.
- n. Transvaginal ultrasound will be performed on women who have not undergone a hysterectomy. During screening, the pelvic examination, with assessment of local irritation and cervical screening (if needed), should be performed prior to the transvaginal ultrasound.
- o. Participants will be required to engage in vaginal intercourse or other sexual activity (masturbation, etc.) at least 1 time between Days 49-56, and complete an assessment of VVA symptoms in their diary.

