13.1.4 Safety and Tolerability Analyses

Safety analyses will be conducted using data from the safety population (as defined in Section 13.1.1). Descriptive statistics will be calculated for safety data and presented by visit and treatment group for quantitative safety data, and frequency counts will be compiled for classification of qualitative safety data. Safety variables include treatment-emergent adverse

events (TEAEs), clinical laboratory values, vital signs, ECG readings, physical examination results, endometrial thickening in women who have not undergone hysterectomy, and prior and concomitant medications. No formal inferential analyses will be conducted for safety variables, unless otherwise noted.

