13.1.4.1 Adverse Events

All AEs will be coded using the Medical Dictionary for Regulatory Activities (MedDRA), Version 24.0 or higher.

An AE is defined as treatment emergent if the first onset or worsening is after the first administration of IP (DARE-VVA1) and not more than 30 days after the last administration of IP.

The number and percentage of participants with TEAEs will be displayed for each treatment group by system organ class and preferred term. Summaries of TEAEs by severity and relationship to IP will also be provided. All TEAEs leading to IP discontinuation and/or study discontinuation will be summarized separately.

Serious adverse events will be summarized separately in a similar manner by treatment group. Summaries of SAEs by severity and relationship to IP will also be provided. Participant listings of AEs, SAEs, and AEs causing discontinuation of IP will be produced.

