13.1.4.2 Clinical Laboratory Evaluations

Descriptive summaries (mean, SD, median, minimum, and maximum) of actual (absolute) values and changes from baseline values will be presented for clinical laboratory values by treatment group at each time point.

The number of participants with clinical laboratory values categorized as below, within, or above normal ranges will be tabulated showing change from baseline (shift tables) for each clinical laboratory analyte by treatment group and by study visit.

Laboratory values that are outside the normal range will also be flagged in the data listings and presented with the corresponding normal ranges. Any out-of-range values that are identified by the investigator as being clinically significant will also be shown in a data listing.

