13.1.4.5 Local Site Irritation

Change in local irritation scores (for erythema and edema, see [Table 10-1](#)) from baseline to Day 57 will be calculated. Descriptive summaries (mean, SD, median, minimum, and maximum) will be provided for absolute values and for change from baseline by treatment group. In addition, number and percentages of participants with each score will be summarized categorically for erythema and edema separately.

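### The only scored local-irritation endpoint is the change to Day 57; a per-woman worst-score summary should be added

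*Combined protocol and SAP*

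**What the plan says.** Section 6.4 names one scored irritation endpoint for the first primary objective: "Change in local site irritation scores from baseline to Day 57". Section 13.1.4.5 repeats it, stating that the change in the erythema and edema scores "from baseline to Day 57 will be calculated". It adds descriptive statistics for absolute values and change by treatment group, and says that the "number and percentages of participants with each score will be summarized categorically for erythema and edema separately". It names no visits for that categorical table.

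Section 13.1.4 sets the general rule that descriptive statistics are "presented by visit and treatment group for quantitative safety data", with frequency counts for qualitative data, in the Safety population.

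The scores are collected often. Footnote e to Table 2-1 reads: "Vaginal speculum examinations will include assessment of local irritation (scoring of erythema and edema), and a full pelvic examination".

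Irritation also has an adverse-event (AE) route. The Synopsis says: "Any irritation, discharge or pain will be reported as an adverse event (AE". For treatment-emergent adverse events (TEAEs), Section 13.1.4.1 says: "The number and percentage of participants with TEAEs will be displayed for each treatment group by system organ class and preferred term". The Synopsis (in a later paragraph) and Section 10.3.1.2.4, however, speak of reporting those speculum abnormalities that are judged clinically significant.

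Section 13.1 describes itself as a summary and leaves the detail to an SAP to be written before database lock. The document reviewed holds no further SAP text on local irritation.

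**The concern.** Local tolerability is a central question for a vaginal insert being given to humans for the first time. Section 7.2 says that placebo is included to separate effects of tamoxifen from those of the excipients or of the insert itself. With 8 women per group and descriptive comparisons, a natural summary is how many women in each group ever had a new or worse score than at baseline.

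The plan's scored endpoint does not answer that. It is a single reading at the end of treatment, six weeks after daily dosing stops. Irritation that appears under daily dosing and has cleared by Day 57 does not show in it. Nor does a score from a woman who leaves the study before Day 57.

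**Working it through.** The plan states no figure for this point, so there is none to reproduce. The check takes three steps.

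**1. When the scores are taken.** Inputs: the speculum row of Table 2-1 with footnote e, and the dosing schedule in Section 7.1.
- Baseline side: Screening and Day 1 before the dose.
- Scheduled post-baseline: Day 2 (24 hours), Days 7, 18, 28, 42 and 57, and follow-up (Day 63). That is 7 scorings, 5 of them before Day 57. Early Termination adds one for women who leave.
- Dosing is daily for two weeks and then twice weekly for six. Only the Day 2 and Day 7 scorings fall in the daily phase, and neither enters the Day 57 endpoint.

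**2. What by-visit tables can and cannot show.** Take the favourable reading, that scores are tabulated at every visit. Let n be the group size and c_k the number of women with a score of 1 or more at visit k. The number of women ever affected lies between

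lower = max(c_k) and upper = min(n, sum of c_k).

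The counts below are illustrative, not predictions.
- n = 8, one woman at each of three visits: max = 1, min(8, 3) = 3. Range 1/8 = 12.5% to 3/8 = 37.5%.
- n = 8, one woman at each of all seven visits: max = 1, min(8, 7) = 7. Range 1/8 = 12.5% to 7/8 = 87.5%.
- n = 4 (one hysterectomy stratum of a group; Section 13.1.1 asks for all analyses by stratum), one woman at each of three visits: 1/4 = 25% to 3/4 = 75%.
- A dose group and placebo, both with 1 of 8 at three visits: the difference in women ever affected runs from (1 − 3)/8 = −25 to (3 − 1)/8 = +25 percentage points.

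If positive scores fall at no more than one visit, the count is fixed and the problem disappears. Score counts also do not separate new findings from those present at baseline. The mean, median, minimum and maximum change show at most that somebody worsened, not how many did.

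**3. What the AE route adds.** Set side by side:
- Section 11.1.1 counts any unfavourable sign, and the worsening of a pre-existing condition, as an AE.
- Section 11.2 captures local reactions, and records deterioration of a condition present at screening.
- Section 11.2.2.1 has a Grade 1 for events that are easily tolerated, so mild events are in scope.
- Sections 11.1.6 and 13.1.4.1 define treatment-emergent as first onset or worsening, and count participants.
- The Synopsis treats any irritation as an AE.
- Against these, the Synopsis and Section 10.3.1.2.4 tie the reporting of speculum findings to clinical significance.

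The TEAE table should therefore hold most new or worsened irritation, per woman and at any time. What remains open is a mild erythema or edema score that the investigator judges not clinically significant. The table is also organised by coded term, not by score.

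**The case against.** The strongest reply is that a per-woman, any-time count already exists. The AE definitions are broad, mild events are graded, worsening counts, and TEAEs are summarised in the Safety population, so women who leave early or are replaced (Section 8.5) stay in. All CRF data are listed, so the score count can be rebuilt from about eight women's records per group. Section 13.1 calls itself a summary, and a worst-value table is ordinary SAP detail. Much of this stands, and it limits the point to an improvement.

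It also rules out several stronger readings that a reader might infer:
- *That scores before Day 57 go unanalysed.* Sections 13.1.4 and 13.1.4.5 together can be read as by-visit summaries. Section 13.1.4.2 says laboratory summaries "will be presented for clinical laboratory values by treatment group at each time point" and the irritation section does not, but the vital-signs section omits it too, so the contrast carries little weight.
- *That transient irritation would escape any per-woman count.* The TEAE table should catch most of it.
- *That the AE rules flatly contradict each other.* The Synopsis sentence is about irritation; the clinical-significance wording is about speculum findings in general. Both can stand, with doubt only over mild scores. The sentence in Section 10.3.1.2.4 that names local AEs and local irritation separately concerns optional photographs and is not a rule for AE entry.
- *That data from early leavers are lost.* Section 8.4 keeps women who stop the product in the study where they are willing, and the Early Termination visit includes the scoring. Nothing excludes those scores from a summary; none is said to include them.

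The objection does not supply a planned summary of the scores themselves by woman, or a clear rule for mild scores.

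**Conclusion.** The point holds as a low-cost improvement. The only scored irritation endpoint for a primary objective is a single late reading, while seven scheduled post-baseline scorings are collected. By-visit tables, if produced, leave the number of women affected open whenever positives occur at two or more visits: 1 to 3 of 8 in the three-visit example. The TEAE table narrows this, but its entry rule for mild scores is unclear.

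The bounds in the working need no assumed rate of irritation, but they are extremes for illustrative counts. The documents give no rate from which to say how often the ambiguity would arise. The conclusion applies to the plan as supplied; a later SAP may settle it. No planned analysis is invalid.

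**What to change.** In Section 13.1.4.5 or the SAP, add for the Safety population, by treatment group with placebo alongside, the number and percentage of women:
- by worst post-baseline erythema score;
- by worst post-baseline edema score;
- with any increase from baseline in each.

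Count every post-baseline examination, including Early Termination and unscheduled ones. Keep the Day 57 change as a supporting summary. Reconcile the Synopsis sentence on irritation with the clinical-significance wording in the Synopsis and Section 10.3.1.2.4, so that sites know which irritation findings are recorded as AEs.

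The cost is some wording and one more table from data already collected. The downside is that a worst score over several visits picks up more background irritation than a single visit, so it must be read against placebo. It also cannot see irritation that comes and goes between examinations, such as in the 18 − 7 = 11 days between the Day 7 and Day 18 visits; that still depends on AE reporting.
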